9.2.1 Immunogenicity Testing

Frequency and percentages of positive anti-drug antibodies (ADA) and neutralizing antibodies (NAb) will be summarized by scheduled visit, and overall treatment received. Additionally, immunogenicity data will be presented in a data listing.

9.3 Vital Signs

Descriptive summaries of actual (absolute) values and changes from baseline will be presented for all vital signs (temperature, systolic blood pressure, diastolic blood pressure, heart rate),

weight, height, and BSA will be presented by visit and overall treatment. These data will be presented in a data listing by subject.

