Infections and Infestations—upper respiratory tract infection.

Investigations—blood alkaline phosphatase increased, liver function tests abnormal/ elevation of hepatic enzymes, increased triglycerides, and weight decreased.

Metabolic—hyponatremia, hypokalemia, hyperglycemia, and hypertriglyceridemia.

Musculoskeletal—back pain, clubbing, and muscle spasms.

Nervous System—dizziness (excluding vertigo), gait disturbance, headache, Parkinsonian symptoms, convulsion/seizure (including grand mal convulsions), and transient ischemic attacks.

Psychiatric—confusion, depression, disorientation, hallucinations, mental status changes, and mental status decreased.

Pulmonary—tachypnea, bronchospasm, pulmonary edema, and interstitial pneumonitis.

Renal—acute renal failure (which may be reversible) and proteinuria.

Skin and Subcutaneous Tissue Disorders—atopic dermatitis, (exacerbation of) dermatomyositis, transient cutaneous rash, and urticaria.

Vascular Disorder—deep venous thrombosis, hypotension, pulmonary embolism.

Abnormal Laboratory Test Values: Elevations of ALT and AST have been observed [*see Warnings and Precautions (5.4)*].

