6.2 Postmarketing Experience

The following adverse reactions have been identified during post approval use of ACTIMMUNE. Because these reactions are reported voluntarily from a population of uncertain size, it is not always possible to reliably estimate their frequency or establish a causal relationship to drug exposure.

Children with CGD less than 3 years of age:

Data on the safety and activity of ACTIMMUNE in 37 patients under the age of 3 years was pooled from four uncontrolled postmarketing studies. The rate of serious infections per patient-year in this uncontrolled group was similar to the rate observed in the ACTIMMUNE treatment groups in controlled trials. Developmental parameters (height, weight and endocrine maturation) for this uncontrolled group conformed to national normative scales before and during ACTIMMUNE therapy.

In 6 of the 10 patients receiving ACTIMMUNE therapy before age one year 2-fold to 25-fold elevations from baseline of AST and/or ALT were observed. These elevations occurred as early as 7 days after starting treatment. Treatment with ACTIMMUNE was interrupted in all 6 of these patients and was restarted at a reduced dosage in 4. Liver transaminase values returned to baseline in all patients and transaminase elevation recurred in one patient upon ACTIMMUNE rechallenge. An 11-fold alkaline phosphatase elevation and hypokalemia in one patient and neutropenia (ANC = 525 cells/mm³) in another patient resolved with interruption of ACTIMMUNE treatment and did not recur with rechallenge.

In the postmarketing safety database clinically significant adverse reactions observed during ACTIMMUNE therapy in children under the age of three years (n=14) included: two cases of hepatomegaly, and one case each of Stevens-Johnson syndrome, granulomatous colitis, urticaria, and atopic dermatitis.

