6. GENERAL ISSUES FOR STATISTICAL ANALYSIS

Data processing, tabulation of descriptive statistics, calculation of inferential statistics, and graphical representations will be performed using SAS® Software (release 9.3 or higher) for Windows, unless otherwise specified.

Continuous (quantitative) variables will be summarized using descriptive statistics including number of non-missing values, mean, standard deviation (SD), median, minimum, and maximum.

Categorical (qualitative) variables will be summarized using the number and proportion of each possible value. In general, the denominator for the percentage calculation will be based upon the total number of subjects in the study population for the treatment group.

The minimum and maximum will be reported with the same degree of precision (i.e., the same number of decimal places) as the raw data. Measures of location (mean and median) will be reported to 1 degree of precision more than the raw data and measures of spread (standard deviation) will be reported to two degrees of precision more than the raw data.

Assessments done on unscheduled visits will not be summarized but will be listed. All analyses will be completed on the Safety Population unless otherwise specified. Additionally, all summaries will be presented by overall treatment.

All final, planned analyses identified in the protocol and in this SAP will be performed after all relevant study data have been processed and integrated into the analysis database, analysis populations have been finalized, and the database has been locked. Any post-hoc, exploratory analysis completed to support planned study analyses, which were not identified in this SAP, will be documented and reported in Section 9.8 of the CSR. Any results from these unplanned analyses (post-hoc) will also be clearly identified as subject in the text of the CSR.

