6.3 Derived and Computed Variables

The following derived and computed variables have been initially identified as important for the analyses of Safety, Efficacy and Exploratory endpoints. It is expected that additional variables may be required. The SAP will not be amended for additional variables that are not related to the primary target or key secondary target variables. Any additional derived or computed variables will be identified and documented in the SAS programs that create the analysis files. If the SAP is not amended, further derivations related to primary and secondary target variables will be described in the CSR.

- 302 Baseline = The last non-missing measurement/assessment on the date of Week 26 Visit from HZNP-ACT-301. If this measurement is missing or otherwise unavailable, it will be the last non-missing measurement/assessment on or prior to first dose in HZNP-

ACT-302.

- 301 Baseline = The last non-missing measurement/assessment prior to first dose of Study in HZNP-ACT-301.
- Study Day = Assessment Date – Date of Enrollment + 1
- Change from Baseline = Value at Post-Baseline – Value at Baseline
- Concomitant Medication is defined as any medication a subject has received concurrently with study treatment.
- Prior Medication is defined as any medication or therapies initiated prior to date of first dose of study drug. Medications that are started prior to the date of first dose of study drug and continue after the first dose of drug are considered to be both prior and concomitant medications.
- Treatment-Emergent Adverse Event (TEAE) – A TEAE is any adverse change from the subject's baseline condition that occurs on or after the date of the first dose of study drug through the duration of the clinical study.
- Related TEAE – Any TEAE with a reported relationship to study drug of 'possibly related'.
- Compliance = Calculated as the percentage of the number of vials used divided by the expected number of vials used, where the number of vials used is the number of used vials returned.

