9.4 Electrocardiogram (ECG) and Echocardiogram

Descriptive summaries of actual (absolute) values and changes from baseline will be presented for ECG quantitative measures (heart rate, PR interval, QRS duration, QT interval and QTC interval). These data will be summarized by visit and overall treatment.

Additionally, the frequency and percentage of subjects with normal, abnormal not clinically significant, and abnormal clinically significant ECGs will be summarized by visit. Shift tables will also be presented and display the number of subjects who had values that shifted from their baseline result.

Echocardiogram data will be summarized for left ventricular hypertrophy, left ventricle dilated, ejection fraction (%), PWTd (cm), IVSTd (cm), LVOT peak velocity (m/sec), LVOT obstruction (y/n).

Left ventricular hypertrophy, left ventricle dilated and LVOT obstruction will be counted by the frequency and percentage of subjects with, without, and unknown within ventricular category. Ejection fraction, PWTd (cm), IVSTd (cm), and LVOT peak velocity (m/sec), will be summarized by descriptive statistics.

ECG and Echocardiogram data will be presented by subject in separate data listings.

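### SAP 9.3 summarises weight and height only on the raw scale, pooled over growing children and adults, so normal growth can offset a drug-related weight loss in the mean and median

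*SAP*

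**What the plan says.** SAP 9.3 opens with "Descriptive summaries of actual (absolute) values and changes from baseline will be presented for all vital signs" and continues, in a sentence whose grammar is broken, that "weight, height, and BSA will be presented by visit and overall treatment". I read the actual values and changes as covering weight, height and BSA too. It adds: "These data will be presented in a data listing by subject".

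SAP 6.3 defines change as a plain difference: "Change from Baseline = Value at Post-Baseline – Value at Baseline". SAP 6 lists the statistics for continuous variables as "number of non-missing values, mean, standard deviation (SD), median, minimum, and maximum", and groups all summaries by overall treatment. The synopsis of the protocol (Statistical Analyses) calls for summaries by the treatment received in HZNP-ACT-301 as well as overall. SAP 10 records only the removal of the efficacy analyses as a change from plan.

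Protocol Table 7.1 gives the age range as 10 to 25 years at the start of HZNP-ACT-301. SAP 7.3 defines two age categories, 10-16 and 17 and above, but uses them only for demographics. Protocol 9.4.8 confirms that there is no control arm. Protocol 9.5.3.4 schedules height and weight at Baseline and Weeks 4, 13 and 26 (or premature withdrawal).

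The label in Protocol 17.2 (its section 6.1) includes, among potentially related reactions under Investigations, "increased triglycerides, and weight decreased".

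**The concern.** A raw weight change mixes two things: what the drug does, and what the subject would have gained or lost anyway. In adults the second part is small over 26 weeks. In a 10- to 16-year-old it is normally a gain. When both groups share one column and there is no comparator, nothing in the table separates the two parts. A mean near zero could mean no effect, or a loss that growth has filled in.

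Long-term safety is the primary objective (Protocol 8.1), and SAP 2.2 and 8 reduce the report to an abbreviated safety CSR, so the safety tables are what the analysis will deliver. The label says toxicity depends on dose. The study titrates to at most 100 µg/m² against the labelled 50, and Protocol 9.2 says the safety profile at 100 µg/m² is not known in paediatric subjects with FA. A labelled reaction should therefore be readable from the planned tables. SAP 9.2 already judges laboratory values against normal ranges; weight and height have no equivalent reference.

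**Working it through.** The plan states no expected growth, weight-loss threshold or sample size, so there is no figure of its own to reproduce. The check is of the mechanism. Every numerical input below is an assumption.

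**Inputs (assumed)**
- f, share of subjects still growing: 0.3 to 0.7
- g, their normal weight gain in 26 weeks: 1 to 3 kg
- L, mean drug-related loss, the same in all subjects

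**Step 1: raw mean.** Raw mean change = f × g − L. It is zero when L = f × g, so f × g is the loss that is fully hidden in the mean:

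| f | g = 1 kg | g = 2 kg | g = 3 kg |
|---|---|---|---|
| 0.3 | 0.3 | 0.6 | 0.9 |
| 0.5 | 0.5 | 1.0 | 1.5 |
| 0.7 | 0.7 | 1.4 | 2.1 |

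The hidden loss runs from 0.3 to 2.1 kg. For a fixed L = 1 kg, the raw mean runs from 0.3 − 1 = −0.7 kg to 2.1 − 1 = +1.1 kg, so its sign does not identify the effect. For L = 2 kg it runs from 0.3 − 2 = −1.7 kg to 2.1 − 2 = +0.1 kg.

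**Step 2: the other planned statistics.** A simulation (4,000 runs per setting; N = 40, 60 or 80; g = 2 kg; f = 0.3, 0.5 or 0.7; individual SD 1.5 kg) set L at the break-even values 0.6, 1.0 and 1.4 kg.
- Raw mean: within 0.01 kg of zero.
- Raw median: −0.05 to +0.05 kg.
- Average minimum: −3.63 to −4.36 kg.
- Mean of observed minus expected change: about −0.6, −1.0 and −1.4 kg, which recovers the loss.

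The minimum shows individual losers but does not say whether the drug is the reason. The loss is uniform, so removing it raises each minimum by L. The minima with no drug effect then run from −4.03 + 0.6 = −3.43 kg (N = 80, f = 0.3) to −3.88 + 1.4 = −2.48 kg (N = 40, f = 0.7).

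**Step 3: failure to gain.** A child expected to gain 2 kg who gains none has a raw change of 0 kg. That is not negative and not an unusual minimum, and it may prompt no adverse event report.

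**Step 4: height.** Take a normal gain of 1.5 to 3.5 cm in 26 weeks (assumed) and f as above. The raw mean without any effect is 0.3 × 1.5 = 0.45 cm to 0.7 × 3.5 = 2.45 cm. If growth were halved, it would be 0.5 × 0.45 = 0.225 cm to 0.5 × 2.45 = 1.225 cm. It stays positive, and the two ranges overlap. This shows only what the table could not detect; it is not evidence of an effect.

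**The case against.** The strongest reply is that the plan gives far more than a mean. It reports the median, minimum and maximum, and it lists every subject. Weight decrease is an adverse reaction term, and Protocol 9.5.3.1.1 counts clinically significant abnormalities in physiological testing or on physical examination as adverse events. SAP 9.1 tabulates these by preferred term, severity and relationship. This stands for absolute loss in an individual. It does not cover failure to gain, and the adverse event route depends on the investigator's judgement of clinical significance.

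The size of the masking is wholly assumed. Within the ranges used, a 2 kg mean loss is fully hidden only at the extreme corner (0.7 × 3 = 2.1 kg). This stands too.

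Z-scores rest on general-population norms. Protocol 7.1 associates FA with scoliosis, cardiomyopathy and diabetes, which could themselves move height or weight. Without a control, a drift in z-score cannot be attributed to the drug. That limits interpretation, but the raw change has the same limit and normal growth on top of it.

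SAP 12 lets output shells be updated separately, SAP 1 and 4.2 allow labelled post-hoc analyses, and the list of planned tables cannot be read in the public copy, so a further split cannot be excluded. The point rests on the SAP text, which specifies none; a prespecified summary is also more useful than a post-hoc one.

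**Conclusion.** The concern holds in a limited form. Weight and height are summarised only on the raw, unstandardised scale, pooled over children and adults, with no control arm and no age split. Normal growth can offset a labelled reaction in the mean and median. Under the assumed age mix and growth, a mean loss of 0.3 to 2.1 kg would read as zero. This is an inexpensive improvement to a descriptive safety report, not a flaw that invalidates it.

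Four stronger readings are tempting, and the documents do not support them.
- A reader might infer that drug-related weight loss would be invisible. The minimum, the listing and adverse event reports still show individual loss.
- A reader might infer that slowed growth is a documented risk. The label's only statement on growth is that height, weight and endocrine maturation "conformed to national normative scales before and during ACTIMMUNE therapy", in an uncontrolled group under 3 years of age. That is a precedent for using norms, not a signal of harm.
- A reader might infer that children are the most exposed to weight decrease. The label gives no age breakdown for it.
- A reader might extend the point to the SAP 9.4 echocardiogram summaries ("Ejection fraction, PWTd (cm), IVSTd (cm), and LVOT peak velocity (m/sec), will be summarized by descriptive statistics") and ask for wall thickness indexed to BSA. BSA is proportional to the square root of height × weight (Protocol 9.4.7.2). A 5% weight loss multiplies BSA by √0.95 = 0.975 and so raises the index by 1/0.975 − 1, about 2.6%, with no cardiac change. That extension is not recommended.

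**What to change.** In SAP 9.3:
1. Show weight and height change by the existing age categories (10-16; 17 and above), stating the date at which age is taken. This alone removes much of the pooling problem and needs no growth reference.
2. For subjects under 18 at HZNP-ACT-302 Baseline, add age- and sex-standardised z-scores for weight and height by visit, with change from Baseline, using a named growth reference.
3. For all subjects, add the number and percentage whose weight falls from Baseline by more than a prespecified amount at any scheduled visit. At least 5% is one option; that figure is our suggestion and has no source in the documents.
4. Present these also by HZNP-ACT-301 treatment, as the protocol synopsis states. For subjects on active drug in HZNP-ACT-301, the extension Baseline follows 26 weeks of treatment, so any earlier loss is already contained in it.

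The cost is SAP wording, a few more tables and the choice of a growth reference. Height and weight are already collected, and age and gender are already tabulated. The text should say that z-score changes are descriptive and, without a control, may partly reflect FA itself.

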9.4 Electrocardiogram (ECG) and Echocardiogram

Descriptive summaries of actual (absolute) values and changes from baseline will be presented for ECG quantitative measures (heart rate, PR interval, QRS duration, QT interval and QTC interval). These data will be summarized by visit and overall treatment.

Additionally, the frequency and percentage of subjects with normal, abnormal not clinically significant, and abnormal clinically significant ECGs will be summarized by visit. Shift tables will also be presented and display the number of subjects who had values that shifted from their baseline result.

Echocardiogram data will be summarized for left ventricular hypertrophy, left ventricle dilated, ejection fraction (%), PWTd (cm), IVSTd (cm), LVOT peak velocity (m/sec), LVOT obstruction (y/n).

Left ventricular hypertrophy, left ventricle dilated and LVOT obstruction will be counted by the frequency and percentage of subjects with, without, and unknown within ventricular category. Ejection fraction, PWTd (cm), IVSTd (cm), and LVOT peak velocity (m/sec), will be summarized by descriptive statistics.

ECG and Echocardiogram data will be presented by subject in separate data listings.

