7. INTRODUCTION

7.1 Scientific Background

ACTIMMUNE (interferon [IFN]- γ 1b) is an orphan drug product currently approved and indicated for reducing the frequency and severity of serious infections associated with chronic granulomatous disease (CGD) and for delaying the time to disease progression in patients with severe, malignant osteopetrosis (SMO); it is approved under Biologics License Application (BLA) 103836, and is now being studied by Horizon in the treatment of FA.

FA is an autosomal recessive disorder associated with progressive ataxia, cardiomyopathy, scoliosis, diabetes, and loss of visual and sensorineural hearing function at later stages of the disease [Harding, 1981; Lynch et al, 2002a]. FA has a prevalence of about 1 in 50,000 persons in the US [Tsou et al, 2009]. Patients develop difficulty walking, loss of coordination, and dysarthria. Degeneration of the dorsal root ganglion (DRG) neurons, their axons in the dorsal columns, and the dorsal spinocerebellar pathways gives rise to loss of proprioception and associated ataxia. A few other nuclei (including the dentate of the cerebellum) within the central nervous system are affected and contribute to the ataxia [Simon et al, 2004]. The abnormal gene in FA and its product (frataxin) provide insight into pathophysiological mechanisms in this disease. In 98% of individuals, FA is caused by homozygous expanded guanine – adenine – adenine (GAA) repeats in the frataxin gene (*FXN*). This triplet repeat is located within an intron, leading to decreased ribonucleic acid (RNA) transcription and levels of the mitochondrial frataxin protein. Decreased frataxin expression is implicated in the assembly and repair of mitochondrial iron-sulfur-cluster containing enzymes and the ability to produce adenosine triphosphate (ATP) [Babcock et al, 1997; Koeppen, 2011; Rotig et al, 1997]. Frataxin deficiency leads to mitochondrial iron accumulation. This may initiate or propagate free radical reactions leading to cell death, consistent with mitochondrial dysfunction as a pathophysiological mechanism in FA.

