5 WARNINGS AND PRECAUTIONS

5.1 Cardiovascular Disorders

Acute and transient "flu-like" symptoms such as fever and chills induced by ACTIMMUNE at doses of 250 mcg/m²/day (greater than 10 times the weekly recommended dose) or higher may exacerbate pre-existing cardiac conditions. Patients with pre-existing cardiac conditions, including ischemia, congestive heart failure or arrhythmia on ACTIMMUNE should be monitored for signs/symptoms of exacerbation. Some of the "flu-like" symptoms may be minimized by bedtime administration of ACTIMMUNE. Acetaminophen may also be used to ameliorate these effects.

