2.2.1 Safety Endpoints

Adverse event and concomitant medication data will be summarized. Clinical laboratory safety data, vital sign data, echocardiogram data, and ECG interval data will be summarized with descriptive statistics for Baseline of HZNP-ACT-302, post-dose, and change from Baseline of HZNP-ACT-302 to post-dose values. Shift tables will be presented for clinical laboratory values and ECG categorical results from Baseline of HZNP-ACT-302 to each post-dose visit. Physical examination findings will be listed by subject. Results of immunogenicity testing will be presented in tabular format.

[figure not shown]

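### The three categorical echocardiogram findings are summarised only as separate counts, so the SAP's tables can bound but not report how many subjects newly develop one

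*SAP*

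**What the plan says.** Protocol 9.5.3.5 schedules an echocardiogram twice: at Baseline/Day 1 and at Week 26 or premature withdrawal (PW).

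For the categorical results SAP 9.4 says: "Left ventricular hypertrophy, left ventricle dilated and LVOT obstruction will be counted by the frequency and percentage of subjects with, without, and unknown". For the continuous ones it says: "Ejection fraction, PWTd (cm), IVSTd (cm), and LVOT peak velocity (m/sec), will be summarized by descriptive statistics".

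In the same section, the paragraph on ECG categories adds: "Shift tables will also be presented and display the number of subjects who had values that shifted from their baseline result". That sentence comes before the echocardiogram text. SAP 2.2.1 is explicit about scope: "Shift tables will be presented for clinical laboratory values and ECG categorical results from Baseline of HZNP-ACT-302 to each post-dose visit". Protocol 9.6.1 limits shift tables in the same way.

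SAP 2.2.1 also makes a general promise that covers echocardiography: "echocardiogram data, and ECG interval data will be summarized with descriptive statistics for Baseline of HZNP-ACT-302, post-dose, and change from Baseline of HZNP-ACT-302". SAP 6.3 defines change from baseline as the post-baseline value minus the baseline value. SAP 6 generally bases percentages on all subjects in the study population. SAP 9.4 ends by providing a by-subject echocardiogram listing.

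**The concern.** The safety question behind a two-visit echocardiogram is who has a finding at the end that was absent at the start. Separate counts at each visit give only the net movement, in which new findings offset findings that resolve or become unreadable.

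Offsetting is plausible here because some entrants may already be affected. Protocol 7.1 states: "FA is an autosomal recessive disorder associated with progressive ataxia, cardiomyopathy, scoliosis, diabetes". The approved label in Protocol 17.2 says flu-like symptoms "may exacerbate pre-existing cardiac conditions", but its section 5.1 ties this to 250 mcg/m²/day or more. The label Highlights carry a cardiac warning without a dose. This is context for monitoring, not evidence of cardiac harm at the doses planned here.

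Long-term safety is the primary study objective (Protocol 8.1), and SAP 2.2 and 8 have removed all efficacy analysis. The safety tables are now the main product of the report.

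**Working it through.** The plan states no figure on this point, so there is none to reproduce. The check asks what the planned counts can say about new onset.

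**Inputs.** From the documents: two visits; three categories (*with*, *without*, *unknown*); a denominator that in general includes everyone; change defined as a subtraction. Assumed, because the documents give neither: the number of subjects (20 to 80) and the share affected at Baseline (25% or 50%), with no unknowns at Baseline. I read the counts as being given at each visit. SAP 9.4 does not say so, but SAP 2.2.1 names Baseline and post-dose.

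**Step 1. Does the change-from-Baseline promise cover the categories?** Subtraction has no meaning for with/without/unknown. SAP 2.2.1 therefore yields a paired summary for the four continuous measures but not for the three categorical ones.

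**Step 2. Limits on new findings.** Let *new* be the number moving from *without* at Baseline to *with* at Week 26.
- Lower limit = max(0, with at Week 26 − with at Baseline)
- Upper limit = min(without at Baseline, with at Week 26)

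For 40 subjects with 25% affected at both visits (10 with, 30 without): lower = max(0, 10 − 10) = 0; upper = min(30, 10) = 10. New onset among the 30 at risk could be 0% or 10/30 = 33%.

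| Subjects (assumed) | New, 25% affected at both visits | New, 50% affected at both visits |
|---|---|---|
| 20 | 0 to 5 | 0 to 10 |
| 40 | 0 to 10 | 0 to 20 |
| 60 | 0 to 15 | 0 to 30 |
| 80 | 0 to 20 | 0 to 40 |

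**Step 3. A falling count does not exclude new findings.** Take 40 subjects with 25% affected at Baseline. At Week 26, 10% (4) are unknown and the *with* count is down by 4, to 6. The upper limit is min(30, 6) = 6, so 0 to 6 could still be new.

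**Step 4. One table, two histories.** Take 60 subjects, 30 with and 30 without at Baseline.
- History A: 5 new, 2 reclassified from with to without, 3 from with to unknown. Week 26: with 30 + 5 − 2 − 3 = 30; without 30 − 5 + 2 = 27; unknown 3. New onset is 5/30 = 16.7%.
- History B: no new findings; 3 go from without to unknown. Week 26: with 30; without 30 − 3 = 27; unknown 3. New onset is 0.

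Both print as 30/27/3. A shift table separates them, because new onset is one of its cells.

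**The case against.** Three stronger readings are tempting, and the documents do not support them.

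- **New findings are hidden.** A reader might infer this, but the listing in SAP 9.4 shows each subject's echocardiogram data, with only two scheduled examinations to compare. Protocol 9.5.3.1.1 also counts clinically significant abnormalities in physiological testing as adverse events. The limitation belongs to the summary tables, not to the whole plan.
- **Unreadable scans pass for resolution.** They do not. A resolved finding raises *without* and an unreadable one raises *unknown*, and these are tabulated separately. In Step 4 two of the three rows move (30/30/0 to 30/27/3). What the rows cannot show is who moved where.
- **Loss of ejection fraction goes unsummarised.** SAP 2.2.1 already commits to Baseline, post-dose "and change from Baseline of HZNP-ACT-302 to post-dose values" for echocardiogram data, and Protocol 9.6.1 says the same. The shorter wording in SAP 9.4 does not withdraw that.

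Two further objections carry weight. The planned-table list cannot be read in the supplied text, so an echocardiogram shift table may already exist there. And the report is descriptive and abbreviated, which limits how much one table matters.

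The safeguards are nevertheless partial. A listing gives no incidence. Adverse-event capture depends on a judgement of clinical significance, and Protocol 9.5.3.1.2 generally excludes events unequivocally due to disease progression unless they are serious or lead to discontinuation. In a disease associated with cardiomyopathy, a new finding could be attributed to the disease. SAP 12 lets the shells be updated independently of the SAP, so the commitment is safer in SAP 9.4.

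**Conclusion.** The point holds for the three categorical findings. As the readable text stands, their summary tables bound new onset but cannot report it, and the bounds are wide: 0 to 10 of 40 subjects when 25% are affected at both visits. The ranges rest on assumed sample sizes and prevalences and show what the tables would leave open; they do not predict results. Two documentary facts carry the conclusion: no paired summary is stated for these categories, and the defined change from baseline cannot supply one. For the continuous measures there is only a difference in wording between SAP 9.4 and 2.2.1. This is a worthwhile, nearly free improvement to a safety report, not a flaw that undermines it.

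**What to change.** In SAP 9.4, and in the shift-table sentence of SAP 2.2.1:

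1. Add a Baseline-by-Week 26 (or PW) shift table for each of left ventricular hypertrophy, left ventricular dilatation and LVOT obstruction, with *unknown* as its own row and column.
2. Report new-onset findings as a count and percentage of subjects who lack the finding at Baseline and have a known post-baseline reading. Show the number excluded as unknown.
3. State that a PW echocardiogram is always the post-baseline reading. SAP 6.1 assigns PW data to the nearest visit at which the item was scheduled. For echocardiography those are Day 1 and Day 183, so a PW scan before their midpoint, Day (1 + 183)/2 = 92, would be nearer to Baseline.
4. As editorial alignment only, repeat in SAP 9.4 that ejection fraction, PWTd, IVSTd and LVOT peak velocity are summarised by visit with change from Baseline.

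The cost is a few sentences and one table shell. Both echocardiograms are already scheduled, so no new data are needed. If the planned-table list already contains such a table, only the SAP text needs to change.
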